- Cervical cancer incidence in women with stable NILM cytology after one year.

Nature and extent of the burden and risks associated with participation, benefit and group relatedness:

As this is a retrospective cohort study using existing screening data, no direct burden, risks, or interventions are associated with study participation. The potential benefit lies at the population level: results may provide evidence to optimize follow-up strategies for HPV-positive women with low-grade cytological abnormalities or persistent NILM results, and for those with relevant medical history, thereby reducing unnecessary procedures while maintaining safe cancer detection.

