2. OBJECTIVES

Primary Objective:

To determine the five-year incidence of histologically confirmed cervical cancer in HPV-positive women with low-grade cytological abnormalities detected through the Dutch cervical cancer screening program.

Secondary Objectives:

- To assess time to cervical cancer diagnosis, all-cause mortality, type of examination at which the diagnosis was established and the histological characteristics of the carcinoma (subtype) in this population , within five years after enrollment.
- To assess cervical cancer risk stratified by histological diagnosis within three months of baseline abnormal cytology (\leq CIN 1 vs CIN 2+) and, for the \leq CIN 1 group, further stratified by cytology at 12-month follow-up (no or nondiagnostic cytology, \leq LSIL, HSIL +), with a follow-up period of five years and three months after enrollment.
- To perform a sub-analysis of women with a history of abnormal cytology or histology and assess their five-year cervical cancer risk.
- To evaluate the incidence of cervical cancer in women with stable NILM cytology after one year and compare it to the five-year incidence in women with low-grade cytological abnormalities.

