4.3 Exclusion criteria

There are no exclusion criteria.

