6.2 Secondary study parameter(s)

Secondary study parameters include:

- Time-to-diagnosis of cervical cancer, which will be displayed in a line diagram with time on the y-axis and number of cases on the x-axis.
- All-cause mortality, type of examination at which the diagnosis was established, and histological subtype of cervical cancer, which will be summarized as frequencies and percentages for each relevant group.
- Cervical cancer incidence in women with stable NILM cytology after one-year follow-up, cervical cancer incidence in women with a history of abnormal cytology or histology, and risk stratification by histology within three months of baseline cytology and follow-up cytology at 12 months. For these parameters, cumulative incidence and incidence rates will be calculated.

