6.3 Other study parameters

Other study parameters include baseline characteristics such as age, which will be assessed for normality using the Shapiro-Wilk test. If normally distributed, this variable will be reported as means with standard deviation (SD). If non-normally distributed, it will be reported as medians with interquartile range (IQR). Cytology and histology results at baseline and follow-up, HPV test results, and relevant medical history will be summarized as frequencies and percentages for each relevant group. For the relevant medical history, the highest histology results will be presented. In case a patient has both cytological and histological results, histology will be prioritized. Pap scores will be converted to Bethesda system classifications using the KOPAC scores.[14] Missing data will be described, and analyses will include all available data.

All statistical analyses will be conducted using SPSS Statistics version 29 (IBM Corp., Armonk, NY, USA, 2025).

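### The history analysis in section 6.2 is not split by severity of the prior abnormality, so it cannot inform follow-up after prior CIN 2+

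*Combined protocol and SAP*

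**What the plan says.** Every place that mentions the history analysis (Summary, sections 2, 5.1.2 and 6.2) defines the group by one yes/no condition. The objective in section 2 is "To perform a sub-analysis of women with a history of abnormal cytology or histology and assess their five-year cervical cancer risk". Section 6.2 lists "cervical cancer incidence in women with a history of abnormal cytology or histology" among several parameters and then states: "For these parameters, cumulative incidence and incidence rates will be calculated". No strata are named for history.

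Section 4.3 states "There are no exclusion criteria", so women with any prior grade are in the group.

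Section 6.3 does grade prior results. It says "For the relevant medical history, the highest histology results will be presented" and adds "In case a patient has both cytological and histological results, histology will be prioritized". It also converts Pap scores to Bethesda classes. The stated use is descriptive: "relevant medical history will be summarized as frequencies and percentages for each relevant group".

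The plan does split cancer risk at CIN 1 versus CIN 2+, but only for histology obtained close to the index smear (a three-month window), not for earlier history.

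On use, the Summary says the results may help to optimise follow-up for the cytology groups "and for those with relevant medical history, thereby reducing unnecessary procedures while maintaining safe cancer detection".

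**The concern.** A woman with one borderline smear years ago and a woman with prior CIN 3 enter the same numerator and denominator. The frequency table in 6.3 will show how many women had each prior grade, but not how many cancers arose in each. A reader who wants the risk after prior CIN 2+ would have only the pooled figure.

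That matters because the Summary names women with relevant history among those whose follow-up the results might inform. If the pooled figure mostly reflects minor histories, it is least informative for the women in whom a falsely reassuring figure would cost most.

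**Working it through.** The documents state no expected incidence, subgroup size or mix of prior grades, so there is no plan figure to reproduce. The check has three parts.

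**1. Text.** The grading in 6.3 is tied to frequencies and percentages. The incidence in 6.2 is tied to the yes/no history group. Nothing links the two. The CIN 1 versus CIN 2+ split elsewhere concerns index histology and does not fill the gap.

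**2. Size of the possible masking.** Let h be the share of history women with prior high-grade disease, and RR their risk relative to women with a minor history. Both are assumptions.

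- Pooled / minor risk = (1 − h) + h × RR
- Pooled / high-grade risk = [(1 − h) + h × RR] / RR

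For h = 0.2 and RR = 4: 0.8 + 0.8 = 1.6, and 1.6 / 4 = 0.40.

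| h | RR | pooled / minor | pooled / high-grade |
|---|---|---|---|
| any | 1 | 1.0 | 1.00 |
| 0.1 | 2 | 1.1 | 0.55 |
| 0.1 | 8 | 1.7 | 0.21 |
| 0.2 | 4 | 1.6 | 0.40 |
| 0.4 | 2 | 1.4 | 0.70 |
| 0.4 | 8 | 3.8 | 0.475 |

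Over h = 0.1 to 0.4 and RR = 2 to 8, the pooled incidence is 1.1 to 3.8 times the minor-history risk and 0.21 to 0.70 of the high-grade risk. The same formulas hold for the incidence rate if h is read as a share of person-years.

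**3. Precision after a split.** Assume 5,000 history women, 20% with prior high-grade disease, and five-year risks of 5.0 and 1.0 per 1,000. Exact (Clopper-Pearson) 95% intervals, per 1,000:

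- High-grade: 5/1,000 = 5.0 (1.6 to 11.6)
- Minor: 4/4,000 = 1.0 (0.3 to 2.6)
- Pooled: 9/5,000 = 1.8 (0.8 to 3.4)

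The high-grade estimate is 5.0 / 1.8 = 2.8 times the pooled one and lies above the pooled upper limit, but its own interval is wide. With 2,000 women and a 10% share, the high-grade row would hold about 1 cancer in 200 women, with an interval of 0.1 to 27.5 per 1,000. A split without intervals could therefore mislead as easily as a pooled figure.

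**The case against.** The strongest case against has four parts.

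- **The objective is met as worded.** It asks for the risk in women with any abnormal history, and one incidence answers that. The result is secondary and descriptive, with no test or decision rule. The primary endpoint is unaffected. This stands, and it is why the point is an improvement and not a flaw in the main analysis.
- **The plan is silent on a split; it does not forbid one.** That is true. Pooling is the natural reading of 6.2, but a reader might infer that the plan rules out severity strata, and it does not. Still, a split chosen after the data are seen would be post hoc.
- **A single highest prior grade is not in fact coded.** A reader might infer from 6.3 that every woman already has one. The text supports less: highest histology is presented, histology overrides cytology, and no rule picks among several smears. A woman with a prior high-grade smear and a biopsy no worse than CIN 1 follows her biopsy under 6.3. A row defined as high-grade cytology or CIN 2+ would put her elsewhere. This stands and shapes the fix.
- **The frequency table limits misreading.** It does so in part: it shows the mix of prior histology but gives no risk by grade.

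The argument that severity is only one of many possible splits carries less weight. The plan itself uses the CIN 1 versus CIN 2+ cut for cancer risk elsewhere and already grades history.

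**Conclusion.** The point holds as a cheap, worthwhile improvement to one secondary analysis. As written, 6.2 yields no cancer risk specific to prior CIN 2+, and neither the pooled incidence nor the 6.3 table can support the Summary's aim for that group.

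The understatement is conditional. It requires that high-grade histories carry higher risk, and it is largest when they are a small share. Under the assumed ranges the pooled figure is 0.21 to 0.70 of the high-grade risk, and at equal risk there is no masking.

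A reader might infer that the pooled figure will be driven by minor histories, or that the plan will declare reduced follow-up safe after prior high-grade disease. The documents support neither. They give no mix and no risk by prior grade, state no safety threshold, and say only that the results may provide evidence.

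**What to change.** In section 6.2, replace the single history line with two prespecified rows and a pooled total:

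- **Classification.** Follow the 6.3 rule. Use the highest prior histology where there is any (up to CIN 1 versus CIN 2+). Otherwise use the highest prior cytology (low-grade versus high-grade).
- **Discordant women.** Count separately those with a prior high-grade smear but histology only up to CIN 1, and show the result again with them moved to the high-grade row.
- **Reporting.** For each row and the total give cases, women, person-years, cumulative incidence and incidence rate, with exact 95% confidence intervals.
- **Interpretation.** Limit any safety statement about history to the row in which it was estimated.

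The cost is small. The prior results are already to be collected, so no new data are needed, but one classification rule must be added because 6.3 does not say how to choose among several smears. The real downside is few cancers and wide intervals in the high-grade row, which the intervals will make visible.

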6.3 Other study parameters

Other study parameters include baseline characteristics such as age, which will be assessed for normality using the Shapiro-Wilk test. If normally distributed, this variable will be reported as means with standard deviation (SD). If non-normally distributed, it will be reported as medians with interquartile range (IQR). Cytology and histology results at baseline and follow-up, HPV test results, and relevant medical history will be summarized as frequencies and percentages for each relevant group. For the relevant medical history, the highest histology results will be presented. In case a patient has both cytological and histological results, histology will be prioritized. Pap scores will be converted to Bethesda system classifications using the KOPAC scores.[14] Missing data will be described, and analyses will include all available data.

All statistical analyses will be conducted using SPSS Statistics version 29 (IBM Corp., Armonk, NY, USA, 2025).

7. ETHICAL CONSIDERATIONS

7.1 Regulation statement

This study will be conducted in accordance with the principles of the Declaration of Helsinki (2013 version) and in compliance with applicable Dutch laws and regulations. The study was approved by the scientific committee of Palga, the Dutch nationwide pathology databank in the Netherlands (approval number 2025-3). Ethical approval by a medical ethical committee was not required under Dutch law, as no patients were directly involved in the conduct of the research and only non-identifiable data were used.

7.2 Recruitment and consent

No recruitment or informed consent procedures were applicable, as the study uses retrospectively collected, fully anonymized data from Palga.

8. ADMINISTRATIVE ASPECTS, MONITORING AND PUBLICATION

8.1 Handling and storage of data and documents

Data for this study are obtained from Palga (the Dutch nationwide pathology databank). All data and results will be used solely for the purposes described in this study and will not be used for any other purpose or published beyond this scope. The data will not be shared with third parties not involved in the research. Data will be stored securely and will be destroyed five years after publication.

All data are fully anonymized. No procedures will be performed that could reveal the identity of participants if indirectly identifying information is inadvertently included. Access to the data is restricted to the research team. Procedures are in place to ensure data security and participant privacy.

8.2 Amendments

Amendments are changes made to the research after a favourable opinion by the review committee has been given. All amendments will be notified to the review committee that gave a favourable opinion. Non-substantial amendments will not be notified to the review committee, but will be recorded and filed by the sponsor.

8.3 Public disclosure and publication policy

The results of the study will be published in peer-reviewed scientific journals and presented at scientific meetings.

